4.3. Withdrawal or Termination

Participants will be terminated early from the study for the following reasons:

1. The participant elects to withdraw consent from all future study activities including follow up.
2. The participant is “lost to follow up” (i.e., no further follow up is possible because attempts to reestablish contact with the participant have failed).
3. The participant dies.
4. The participant develops a medical condition or is started on a new medication(s) not previously mentioned in the list of prohibited medications that, in the opinion of the investigator, may pose additional risks from participation in the study, may interfere with the participant’s ability to comply with study requirements or that may impact the quality of the data obtained from the study.
5. The participant meets any of the individual stopping rules as delineated.
6. The study is terminated for any reason.

Participants with early termination from this study will not be replaced.

5. Study Procedures

5.1. Schedule of Events

Each subject will have 8 study visits (excluding the general screening visit and wood smoke exposure screening visit to identify responders, which are under separate protocols):

5.1.1. Screening Visits

General Screening: To identify non-asthmatic and asthmatic subjects suitable for WSP exposure, subjects will complete a general screening protocol (UNC IRB approved study #98-0799, *Database and Screening Protocol for Research Studies of the Center for Environmental Medicine & Lung Biology*).

Screening WSP exposure: This protocol will identify subjects who experience a $\geq 10\%$ increase in sputum neutrophilia after WSP exposure, compared to baseline sputum (UNC IRB approved study #15-1775, *To identify persons who are susceptible to WSP-induced inflammation and examine the role of GSTM1 and other factors in this susceptibility*). This protocol involves a detailed review of the subject’s medical history and medication use, lung function (spirometry), collection of an induced sputum sample, and WSP exposure.

5.1.2. Visit 0: Baseline, determine eligibility (at least 1 month after screening WSP exposure):

1. Obtain informed consent.
2. Review any change in medical status since the last visit.
3. Vital signs, oxygen saturation, resting blood pressure
4. Urine pregnancy test for females
5. Physical exam
6. Obtain 12-lead EKG
7. Spirometry
8. Sputum induction
9. Venipuncture (CBC with differential, serum cytokines, serum C-reactive peptide, lipid panel, LDH, fibrinogen, PT, aPTT, INR, gT and metabolite levels).
10. HRV will be collected throughout the entire visit with a Spacelabs monitor. A 30 minute controlled rest will be performed at the end of visit.

5.1.3. Visit 1: Training/Dispense Study Drug (Period 1) (≤ 1 month from baseline visit and at least 1 week prior to V2 Exposure Visit and up to 3 weeks) (we request participants to be fasting for this visit, therefore it is scheduled in the morning)

1. Review any changes in medical status since the last visit.
2. Vital signs, oxygen saturation, and GI symptom questionnaire.
3. Urine pregnancy test for females.
4. Spirometry
5. Baseline flow mediated dilation (FMD) measurement
6. Baseline left ventricular strain (LVS) measurement
7. Volunteers will be trained on the cycle ergometer to reach an exercise level producing a minute ventilation of 20 L/min/m² body surface area (BSA). Subjects will be monitored with a standard 3 lead ECG during exercise.
8. Dispense study drug and symptom diary

5.1.4. Visits 2 (Period 1) and 5 (Period 2): WSP exposure

1. Vital signs, oxygen saturation, resting blood pressure
2. GI and WSP Exposure symptom questionnaire
3. Collect symptom diary
4. Urine pregnancy test for females
5. HRV will be collected throughout the entire visit with a Spacelabs monitor. The monitor will be worn until the 24 hours post exposure visit.
6. Spirometry
7. Venipuncture (CBC with differential, serum cytokines, serum C-reactive peptide, lipid panel, LDH, fibrinogen, gT and metabolite levels)
8. 500 μ g/m³ WSP chamber exposure for 2 hours, with intermittent exercise and rest. Subjects will alternate 15 minutes of exercise on a cycle ergometer (intensity needed to achieve 20 L/min/m² BSA determined at baseline visit) with 15 minutes of rest.
9. Symptom questionnaire (immediately prior to exit from the chamber)
10. Spirometry and resting blood pressure (immediately following exit from the chamber)
11. Lunch - low fat meal is provided. The meal must be the same during each exposure.
12. Obtain 30 minute controlled rest HRV, FMD, and LVS (90 minutes post-WSP exposure)

13. Venipuncture (CBC with differential, serum cytokines, serum C-reactive peptide, lipid panel, LDH, fibrinogen) (4 hours post-WSP exposure)
14. GI and WSP Exposure Symptom questionnaire (4 hours post-WSP exposure)
15. Sputum induction (4 hours post-WSP exposure)

5.1.5. Visit 4: Dispense Study Drug (Period 2) (following 4 week washout and at least 1 week prior to V5 Exposure Visit and up to 3 weeks)

1. Review medical history and adverse events
2. Urine pregnancy
3. Vital signs, oxygen saturation, GI symptom questionnaire
4. Dispense study drug
5. Lung function testing for participants who have asthma

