An additional area of concern was raised by findings from the Coronary Artery Risk Development in Young Adults (CARDIA) study, a population-based observational study. In this study, higher plasma γ T levels in young adults (not taking Vitamin E supplements) were associated with lower lung function measurements (FEV₁ and FVC) (14). However, others have shown that increased *dietary* vitamin E intake had protective effects on lung function in adults (15). Plasma γ T levels have not been significantly associated with risk of asthma or asthma outcomes. However, increased dietary vitamin E, which is predominantly gamma tocopherol (γ T), has been associated with decreased occurrence of asthma in both children (16-18) and adults (19).

Based on our own previous studies, the most common adverse effects of γ T are diarrhea, flatulence, abdominal bloating, and nausea. In our most recent randomized, placebo controlled crossover study evaluating 14 days of γ T-enriched supplementation (1400 mg daily) in 23 adult volunteers with asthma (26), diarrhea was reported in 6 participants (26%) on active treatment, compared to 1 participant (4.3%) on placebo. Nausea was reported in 6 participants (26%) on active treatment, compared to 2 participants (8.7%) on placebo. Bloating and flatulence were reported in 2 participants (8.7%) and 1 participant (4.3%) on active treatment, respectively, with no reports of these symptoms in subjects receiving placebo. One participant withdrew from the study due to intolerable gastrointestinal symptoms. In all other participants, gastrointestinal symptoms were transient in nature, beginning after the first or second dose of study drug and self-resolving despite continued treatment for the 14-day period.

2. Study Objective

The primary objective of this study is to examine the effectiveness of gamma tocopherol for mitigating inhaled WSP-induced airway inflammation in healthy adults and mild asthmatics, specifically airway inflammatory cell recruitment and cytokine production, mucous production, and non-specific bronchial reactivity.

3. Study Design

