3.2. Primary Study Endpoint

The primary endpoint will be change in sputum %PMNs [Δ (postWSP (4 hr) – preWSP)[γ T] vs Δ (postWSP (4 hr) – preWSP)[placebo]] and change in sputum %PMNs [Δ (postWSP (24 hr) – preWSP)[γ T] vs Δ (postWSP (24 hr) – preWSP)[placebo]].

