5.1.6. Visits 3 (Period 1) and 6 (Period 2): 24 hours post-exposure

1. Review any adverse events
2. Vital signs, resting blood pressure, oxygen saturation
3. WSP Exposure symptom questionnaire
4. Venipuncture (CBC with differential, serum cytokines, serum C-reactive peptide, lipid panel, LDH, fibrinogen, PT, aPTT, INR, gT and metabolite levels)
5. Spirometry
6. Sputum induction
7. .

At least a 4 week, but no more than an 8 week washout is required between Period 1 and Period 2.

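### The sputum primary endpoint is written as a pre-to-post change under each treatment, but its only baseline is one shared pre-drug sample, so the paired test compares post-exposure levels

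*Combined protocol and SAP*

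**What the plan says.** Section 3.2 opens with "The primary endpoint will be change in sputum %PMNs" and writes it, at 4 hours and at 24 hours, as post-exposure minus pre-exposure under gamma tocopherol against the same quantity under placebo. Section 6.1 repeats this. Section 2 gives the aim as to "examine the effectiveness of gamma tocopherol for mitigating inhaled WSP-induced airway inflammation".

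Sputum appears in the visit lists as follows:

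- **Section 5.1.2**, headed "Visit 0: Baseline, determine eligibility (at least 1 month after screening WSP exposure": one induction at V0.
- **Section 5.1.3 (V1)**: no sputum. Drug is first handed out here ("Dispense study drug and symptom diary").
- **Section 5.1.4 (V2 and V5)**: no sputum among the items before the chamber, then "Sputum induction (4 hours post-WSP exposure".
- **Section 5.1.5 (V4)**: no sputum before the period 2 drug.
- **Section 5.1.6**, "Visits 3 (Period 1) and 6 (Period 2): 24 hours post-exposure": one induction.

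Blood is handled differently. Section 5.1.4 lists "Venipuncture (CBC with differential, serum cytokines, serum C-reactive peptide, lipid panel, LDH, fibrinogen, gT and metabolite levels" before the chamber and a second draw at 4 hours. No section says which sputum sample is the pre-exposure value.

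**The concern.** The notation suggests that each treatment period has its own before-and-after pair, so that the contrast isolates the rise caused by smoke. For blood neutrophil count, the secondary endpoint in section 3.3, this is so: the same notation is used and an on-treatment pre-exposure draw exists in each period. For sputum it is not so.

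Participants take study drug for seven days before they enter the chamber (section 3.1). If the drug changes resting airway neutrophils in that week, the effect is already present at the start of exposure and is counted as part of the treatment contrast. Both periods use wood smoke and no filtered-air period is scheduled, so nothing else in the sputum data separates the two effects. At stake is the wording of the main conclusion: an effect on the smoke-induced rise, or an effect on the post-exposure level.

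**Working it through.** **1. The plan's own figure.** Section 6.1 gives an effect of 14.5, SD 25.9, alpha 0.05 (two-sided assumed, as sidedness is not stated) and beta = 0.8, read as power 0.80.

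- Paired, normal approximation: (25.9 × (1.960 + 0.842) / 14.5)² = 25.04, so 26.
- Paired t-test (noncentral t): n = 27 gives power 0.7996 and n = 28 gives 0.815. The stated 28 is reproduced exactly.
- An unpaired comparison would need 51 per arm, so 28 implies a paired test.

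**2. Cancellation.** With V0 as the only pre-exposure sputum, for each participant and at either time point:

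(post on drug − V0) − (post on placebo − V0) = post on drug − post on placebo.

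In a simulated data set of 28, the paired t-test gave t = −2.569, p = 0.0160, and the signed-rank test gave p = 0.0204, with or without V0 subtracted. The screening sputum (section 5.1.1) would cancel equally, since it too is drug-free and precedes both periods.

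**3. What the contrast contains.** Let b be the drug's reduction in resting %PMN and r its reduction of the smoke-induced rise. The expected contrast is b + r. An observed 14.5 is therefore compatible with any r = 14.5 − b.

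**4. Size, if r = 0.** The paired t-test has 27 degrees of freedom and noncentrality b × √28 / 25.9. The documents give no value for b, so these shifts are assumptions.

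| Assumed b (points) | Noncentrality | Probability of p ≤ 0.05 |
|---|---|---|
| 2.5 | 0.51 | 0.08 |
| 5 | 1.02 | 0.17 |
| 7.25 | 1.48 | 0.30 |
| 10 | 2.04 | 0.50 |
| 14.5 | 2.96 | 0.81 |

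**5. Where V0 does not cancel.** There are two such cases within section 6.2.

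- *Unpaired t-test.* The text speaks of two-sample tests. In the same simulated data an independent-samples t-test kept the point estimate, but its p-value was 0.011 with V0 subtracted and 0.047 without.
- *Equation 1 with free carryover terms.* In a two-period, two-sequence design these terms leave the treatment effect resting on period 1, between participants. If V0 and post-exposure values have equal variance σ² and correlation ρ, the residual variance is 2σ²(1 − ρ) for the change score and σ²(1 − ρ²) with V0 as covariate. The ratio of standard errors is √((1 + ρ)/2): 0.77, 0.87 and 0.95 for assumed ρ of 0.2, 0.5 and 0.8. The covariate form is never worse, apart from the one degree of freedom it uses.

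Section 6.2 defines every term of Equation 1 except the covariate X_k, so there is already a place for V0.

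**The case against.** The strongest defence is that the randomised crossover still compares post-exposure %PMN without bias, and that this difference is blunting if the drug does not alter resting neutrophils. The documents report no resting effect on neutrophils. They describe the earlier gamma tocopherol findings as effects on challenge-induced neutrophilia (sections 1.1, 1.3 and 6.1). For the planned paired test, restating the endpoint changes no estimate, p-value or sample size. All of this stands.

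It also rules out three stronger readings that a reader might reach:

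- *That the trial cannot show blunting at all.* It can, under the assumption of an unchanged resting level. What it lacks is sputum data to test that assumption.
- *That an old or noisy V0 sample damages the primary result.* V0 drops out of the paired contrast, so neither its age nor its noise matters there. Nor is there a fixed maximum V0-to-V5 interval, because section 5.1.7 allows postponements for illness, missed doses and Covid.
- *That the rejection probabilities predict false claims.* They rest on assumed shifts, and the largest requires the whole planned effect to be a resting effect.

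What the defence does not answer is that the endpoint as written names a quantity that the sputum schedule does not yield separately for each treatment, and that the plan nowhere states the assumption needed to read the result as mitigation.

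**Conclusion.** The point holds as a mismatch between the named endpoint and the quantity estimated. The paired analysis estimates the difference in post-exposure sputum %PMN between treatments. That is a valid treatment effect, and it equals blunting of the smoke response only if resting %PMN is the same on both treatments.

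The possible size depends on an unknown: with no blunting, the chance of a significant result rises from 17% to 81% as an assumed resting reduction goes from 5 to 14.5 points. These figures take 28 completers, a two-sided 5% test and the plan's SD of 25.9. The documents do not say whether that SD belongs to a difference in levels or a difference in changes.

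Exact cancellation assumes a paired test or a mixed model without free carryover terms. Elsewhere, subtracting V0 affects the result. The sample size of 28 is not in question. The plan should be amended, but the data it collects remain usable.

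**What to change.** - **Sections 3.2, 6.1 and 6.2:** define the primary endpoint as the paired within-subject difference in post-exposure sputum %PMN, gamma tocopherol minus placebo, at 4 hours and at 24 hours.
- **Section 6.2:** name V0 %PMN as the covariate X_k in the mixed model, in place of subtracting it, and state that the t-test is paired. With complete data and no carryover term this leaves the treatment contrast unchanged. It helps where V0 does not cancel.
- **Conclusion:** word it as an effect on post-exposure neutrophil level, and state openly that reading it as blunting assumes an unchanged resting level.
- **Supportive check:** prespecify a within-subject comparison of pre-exposure blood neutrophil count by treatment, using V2 and V5 and adjusting for period. Comparing V2 with V5 as such would compare periods, because both treatments occur at each visit (section 6.4). This is a blood proxy, and a null result would not exclude a resting effect in the airway.

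The cost is wording only, with no added visit, induction or sample. The downside is a narrower claim. Keeping the change endpoint instead would need an on-treatment pre-exposure sputum in each period and a fresh look at the sample size, since its variance would depend on a pre-post correlation that the documents do not give.

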6.1 Sample Size Determination

The primary endpoint of this study is Δ sputum %PMNs (post WSP – pre WSP [γ T]) at 4 hour vs (post WSP – pre WSP [placebo]) at 4 hours, and (post WSP – pre WSP [γ T]) at 24 hours vs (post WSP – pre WSP [placebo]) at 24 hours. Preliminary analyses from our screening study of the effects of 500 μ g/m³ WSP exposure on sputum neutrophilia in healthy volunteers and mild asthmatics demonstrated that, among “responders” (those participants with a $\geq 10\%$ increase in sputum neutrophils following WSP exposure), the mean increase in sputum %PMNs was $28.5 \pm 13\%$. In our studies of γ T vs placebo for mitigating LPS-induced change in sputum %PMNs in healthy volunteers (11) and mild asthmatics (26), we found a γ T treatment effect size of $14.5\% \pm 25.9$. Assuming $\beta=0.8$ and $\alpha=0.05$, a sample size of 28 healthy volunteers and mild asthmatics would be required to detect the same γ T treatment effect size. To account for a 25% attrition rate with human studies, we will inflate the sample size to 35 healthy volunteers and mild asthmatics. Importantly, we anticipate that we will decrease subject variability by only recruiting persons with $\geq 10\%$ increase in WSP-induced %PMNs in sputum during the screening protocol (the so-called “responders”).

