6.2. Statistical Methods

Our analytic plan was developed in collaboration with [name], the biostatistician for the CEMALB, who will oversee all statistical analysis. For analysis of sputum and circulating PMN responses as well as cytokine changes within each treatment group, we will use (i) descriptive analysis, (ii) two-sample comparison test, and (iii) random effects regression analysis (Equation 1) designed to take advantage of the crossover design (22). Specifically, we will use the tabular and graphic methods to describe/explore the basic relationship between the groups. We will then follow up by comparing the Δ sputum %PMNs (post WSP – pre WSP [γ T]) vs (post WSP – pre WSP [placebo]) using two-sample tests, either parametric (T-Test) or nonparametric (Wilcoxon signed-rank test), depending on whether the normality assumption is met. We will transform the data to achieve normality if needed. Finally, we will employ a random effect regression modeling technique (Equation 1) that allows us to assess treatment effect while accounting for potential period effect and carry-over effects. This approach is similar to those we have previously described to assess genotype effects (including the GSTM1 null genotype) on response to pollutants (11, 23-25) and is shown below. In all analyses, criterion for significance will be $p \leq 0.05$. To address potential missing data, we will employ multiple imputation methods to address this issue when appropriate; using techniques we have previously described (24).

Linear mixed model approach for global unified analysis of data for secondary and exploratory outcomes:

$$Y_{11k} = \mu + \pi_1 + \tau_1 + \beta X_k + s_{1k} + \epsilon_{11k}; Y_{12k} = \mu + \pi_2 + \tau_2 + \lambda_1 + \beta X_k + s_{1k} + \epsilon_{12k}$$

$$Y_{21k} = \mu + \pi_1 + \tau_2 + \beta X_k + s_{2k} + \epsilon_{21k}; Y_{22k} = \mu + \pi_2 + \tau_1 + \lambda_2 + \beta X_k + s_{2k} + \epsilon_{22k}$$

μ is the grand mean, π_1 and π_2 are period effects, τ_1 and τ_2 are treatment effects, λ_1 and λ_2 are carryover effects for different sequences, s_{1k} and s_{2k} are individual random effects within each sequence, and ϵ 's are random errors. Subscript k is for subjects.

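### Carryover is handled analytically only by weak λ terms, although serum levels already being drawn could check drug clearance directly

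*Combined protocol and SAP*

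**What the plan says.** **Washout.** Section 5.1.6 requires 4 to 8 weeks between periods. The Visit 4 heading in section 5.1.5 reads "Dispense Study Drug (Period 2) (following 4 week washout" and places V4 one to three weeks before the second exposure at V5. V4 lists no blood draw. The documents give no half-life or other basis for the washout length and no criterion for judging that it worked.

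**Analysis.** Section 6.2 first compares the change in sputum %PMNs between treatments with a t-test or Wilcoxon signed-rank test, which makes no allowance for carryover. It then adds a random effects model that "allows us to assess treatment effect while accounting for potential period effect and carry-over effects". Equation 1 contains λ1 and λ2, one per sequence, in Period 2 only. The text applies this model to sputum and blood PMNs, but the caption above the equation assigns it to secondary and exploratory outcomes.

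**Serum levels.** Before the chamber exposure at V2 and V5, section 5.1.4 lists "Venipuncture (CBC with differential, serum cytokines, serum C-reactive peptide, lipid panel, LDH, fibrinogen, gT and metabolite levels". Gamma tocopherol (γT) and metabolite levels are also drawn at V0 (section 5.1.2) and at V3 and V6 (section 5.1.6). Their only stated use is as exploratory endpoint 8 in section 3.3.

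**Sample size.** Section 6.1 takes a treatment effect of 14.5 points with SD 25.9 and concludes that "a sample size of 28 healthy volunteers and mild asthmatics would be required to detect the same" effect.

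**The concern.** If γT or its effect persists into Period 2, participants who took γT first are partly treated during their placebo exposure, and the crossover contrast shrinks toward zero. An analyst who wants to know whether this happened has only the λ terms. These rest on between-subject information, so a λ estimate near zero would say little.

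The terms also have a cost. A two-by-two crossover cannot estimate carryover and still use Period 2 fully for the treatment effect, so keeping λ gives up the within-subject comparison on which the sample size rests.

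Meanwhile, the γT-first group is on placebo at V5, has a V0 level as its own reference, and is the only group in which γT can carry over. The plan collects these measurements but does not name the comparison.

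**Working it through.** **Inputs.** Effect 14.5, SD of the within-subject difference 25.9, power 0.80, α 0.05 and 28 completers come from section 6.1. Two-sided testing is assumed. Section 6.4 randomizes in balanced blocks of 4, so I take 14 completers per sequence. The correlation ρ between a subject's two period responses is not given; I show 0 to 0.7. The visit lists show no sputum sample before exposure at V2 or V5. If V0 is the pre-exposure value for both periods, the shared baseline would tend to make ρ positive, so ρ = 0 is the favourable end.

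**1. The plan's own figure.** The normal approximation gives (1.96 + 0.84)² × (25.9/14.5)² = 25.04, so 26. The noncentral t gives 79.96% power at n = 27 and 81.5% at n = 28. The stated 28 is reproduced as a paired comparison, with SE 25.9/√28 = 4.89.

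**2. The λ contrast.** It compares subject totals between sequences:

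- SD per period: σ = 25.9/√(2(1 − ρ))
- SD of a subject's total: 25.9 × √((1 + ρ)/(1 − ρ))
- SE of the λ contrast: SD of total × √(2/14)
- SE of the treatment estimate with λ kept: σ × √(2/14). A mixed-model fit to simulated data confirmed that this estimate equals the Period 1 between-group difference.

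Power is from the noncentral t with 26 df. The detectable carryover is (1.96 + 0.84) × SE.

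| ρ | σ | SD of total | SE of λ contrast | Power for carryover of 14.5 | Carryover detectable at 80% power | SE of treatment, λ kept | Power for treatment effect, λ kept |
|---|---|---|---|---|---|---|---|
| 0 | 18.3 | 25.9 | 9.8 | 30% | 27.4 | 6.9 | 52% |
| 0.3 | 21.9 | 35.3 | 13.3 | 18% | 37.4 | 8.3 | 39% |
| 0.5 | 25.9 | 44.9 | 17.0 | 13% | 47.5 | 9.8 | 30% |
| 0.7 | 33.4 | 61.7 | 23.3 | 9% | 65.3 | 12.6 | 20% |

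Simulation (20,000 runs each) gave 29.9% at ρ = 0 and 13.2% at ρ = 0.5 for the carryover test.

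**3. Sensitivity of the λ power, at ρ = 0 and ρ = 0.5.**

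- α of 0.10: 42% and 22%.
- All 35 subjects completing: 36% and 15%.
- Per-period SD of 13 (the responder SD in section 6.1): 52% and 38%.
- SD of 13 with α of 0.10: 65% and 51%.

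None reaches 80%.

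**4. Effect of a full undetected carryover.** The mean within-subject difference is 0 in the γT-first sequence and 14.5 in the other. The average is (0 + 14.5)/2 = 7.25. With SE 4.89, power falls from 81% to about 30%.

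**The case against.** The main safeguard is the design, not λ. A 7-day course is followed by at least 4 weeks of washout and at least one more week before the second exposure. That stands. A reader might infer that the plan tests λ and would declare the washout adequate on a non-significant result. Section 6.2 states no such test or rule, so the power figures describe what λ could show, not a decision the plan makes.

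The plan also keeps the simple paired comparison, with its 81% power. With λ in Equation 1 the model already yields the Period 1 contrast, so a sensitivity analysis of that kind exists implicitly. Serum levels are an exploratory endpoint to which Equation 1 would apply, so they are not unanalysed. These points stand. They do not provide the direct V5-versus-V0 check, and they leave the fitted treatment model with the loss shown in the last column of the table.

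The serum check has limits too. With 14 per sequence, a V5-versus-V0 test has 80% power only for a shift of about 0.81 SD of the within-subject change, and a between-sequence comparison on placebo only for about 1.10 SD. A non-significant result would therefore not prove washout, which is why a margin and confidence interval are needed. The V5-versus-V0 comparison assumes a tocopherol-free placebo, whose composition the documents do not give; setting V5 placebo against V2 placebo removes most of that dependence.

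Finally, Equation 1 has an undefined covariate term. Strong prognostic covariates could raise the λ power somewhat, by an amount the documents do not allow one to compute.

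**Conclusion.** The point holds as an improvement to the analysis plan that needs no new data. The λ contrast has about 9% to 30% power for carryover as large as the full 14.5-point effect, for ρ from 0.7 to 0, and about 52% with the responder SD of 13 at ρ = 0. Keeping λ in the treatment model lowers power for the treatment effect from 81% to about 52% (ρ = 0) or 30% (ρ = 0.5). These figures assume 14 completers per sequence, two-sided α of 0.05, no covariate adjustment and the stated range of ρ.

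Three stronger readings are not supported. One is that λ can never detect carryover: its power is low, not nil. Another is that 4 weeks is too short: the documents contain nothing that shows this, and the halving to 7.25 is a worst-case illustration, not a forecast. The third is that cleared serum levels would make Period 2 data trustworthy: they show clearance of drug and metabolites only, and do not exclude a lasting biological effect or carryover from the first smoke exposure.

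**What to change.** In section 6.2:

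1. Prespecify a within-subject comparison of V5 pre-exposure with V0 serum γT and γ-CEHC in the γT-first sequence. Report the estimate and confidence interval against a return-to-baseline margin fixed before unblinding, not a non-significant p-value. Support it with V5 placebo levels in that sequence against V2 placebo levels in the placebo-first sequence.
2. Fit the treatment model with period and treatment but without λ, and report the Period 1 between-group comparison as a sensitivity analysis. State whether the model applies to the primary endpoint, since the text and the equation's caption differ.
3. Draw no washout conclusion from λ.
4. State that serum levels address drug and metabolite clearance only.

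The cost is a short SAP paragraph and a simple analysis. No visit, blood draw or participant is added.
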